Pregnancy Test	X	X						X				X			X	X			X 
ADA (Immunogenicity)		X 						X 							X	X			X 
Hepatitis B, C, CMV 	X														X				X 
PK Sampling	Please refer to Section 8.2 for details of PK samplings																		
Tumor biopsy	X 																		X 
Biomarkers	X		X 								X 				X				
Patient diary handout		X						X											
Patient diary collection		X 						X				X 			X				
Review of patient diary data		X 	X	X	X	X	X	X	X	X	X	X 			X				

Footnotes to Trial Flowchart – Dose Escalation 3Q4W
1 If the patient shows PD, is to start new anti-cancer treatment or withdraws from treatment due to another reason the End of treatment visit should be performed as soon as possible after decision of withdrawal.
2 The visit windows relate to the day of the previous visit. Visit 1 of Cycle 3 and onwards should be performed 7 days ±3 days after Day 22 of the previous cycle.
3 Visit window not applicable for C1V1 and C2V1.
4 Signs, symptoms and diagnosis occurring between Visit 0 and first infusion should be recorded as medical history (see Section 8.4 for details). SAEs should be reported as of the signing of the informed consent.
5 Body weight will be measured on the first dosing day in a cycle, as part of the dose calculation. If body weight is assessed ≤ 7 days before the first day of the planned dosing in a cycle, this weight can be used to calculate dose and is the weight recorded in the eCRF.
6 Temperature, blood pressure and heart rate as according to Section 8.4.8.

Document Name: GCT1021-01 Protocol

Document Number: TMF-03326

Version: 11.0

Footnotes to Trial Flowchart – Dose Escalation 3Q4W
7 All patients will have a CT-scan with contrast of thorax, abdomen, and pelvis performed as part of the screening procedure. If a CT-scan has been performed within 28 days prior to visit CIV1 as part of standard procedure, it is acceptable as screening CT-scan for the trial. If there is suggestion of brain metastases/tumors, a CT-scan of the head will be performed before inclusion.
8 Radiological assessments are to be performed every 8 weeks from CID1. See Section 8.4.7.
9 To be completed as indicated to confirm response, new symptoms, end of treatment visit or at the physician discretion see Section 8.4.7.

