**Footnotes to Trial Flowchart – Expansion**

- 1 If the patient shows PD, is to start new anti-cancer treatment or withdraws from treatment due to another reason the End of treatment visit should be performed as soon as possible after decision of withdrawal.
- 2 The visit windows relate to the day of the previous visit. Visit 1 of Cycle 2 and onwards should be performed 7 days ±3 days after Day 15/22 of the previous cycle.
- 3 Signs, symptoms and diagnosis occurring between Visit 0 and first infusion should be recorded as medical history (see Section 8.4 for details). SAEs should be reported as of the signing of the informed consent.
- 4 Body weight will be measured on the first dosing day in a cycle, as part of the dose calculation. If body weight is assessed ≤ 7 days before the first day of the planned dosing in a cycle, this weight can be used to calculate dose and is the weight recorded in the eCRF.
- 5 Temperature, blood pressure and heart rate as according to Section 8.4.8.
- 6 All patients will have a CT-scan with contrast of thorax, abdomen, and pelvis performed as part of the screening procedure. If a CT-scan has been performed within 28 days prior to visit CIV1 as part of standard procedure, it is acceptable as screening CT-scan for the trial. If there is suggestion of brain metastases/tumors, a CT-scan of the head will be performed before inclusion. Clinical measurement in case of superficial cutaneous lesions should be performed within 28 days prior to visit CIV1 as part of standard procedure. For further details on imaging please refer to Section 8.4.7.
- 7 Radiological assessments and clinical measurements of superficial cutaneous lesions are to be performed every 6 (1Q3W and Cohort 8 3Q4W) or 8 (Cohort 6 3Q4W) weeks (±7days) from C1D1 until disease progression. If treatment is discontinued prematurely, prior to detection of disease progression (e.g., due to an adverse event), every effort should be made that scans continue according to the protocol until disease progression, start of a new anti-cancer treatment, withdrawal of consent or death (see Section 8.4.7 for details).
- 8 To be completed as indicated to confirm response or new symptoms at the end of treatment visit or at the physician discretion.
- 9 TSH, T3 and T4 will only be measured at screening and on Visit 1 of every even cycle.

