#### 8.4.7 Imaging/Computed Tomography

All patients will have a CT-scan with contrast of thorax, abdomen and pelvis performed during screening. If there is suspicion of brain metastases/tumors, a CT-scan of the head will be performed before inclusion. For patients with stable brain metastases enrolled in the expansion part, the CT-scan must include the head and neck.

For patients with superficial cutaneous lesions that are not measurable by a CT-scan, measurement using calipers can be performed, using photographs as documentation.

All sites of metastatic disease should be reported at baseline and followed throughout the trial. Up to 5 target lesions (maximum two per organ) will be defined at screening. A lesion from which a fresh biopsy has been taken during the trial cannot be a target lesion.

Baseline imaging assessments will be performed during the screening period. Any imaging assessments already completed for regular radiographic evaluation of the patient's cancer can be considered as the baseline images for this trial, as long as they are of sufficient diagnostic quality and have been obtained ≤ 28 days prior to C1D1.

Post-baseline scans will be performed every 6 weeks (1Q3W and Cohort 8 3Q4W) or 8 weeks (Cohort 6 3Q4W) (±7 days) from C1D1 until investigator assessed disease progression according to RECIST v1.1. Time points for radiographic evaluation should be calendar based and do not depend on cycle visits i.e. radiological evaluation should be performed regardless of IMP administration delays. For patients who permanently discontinue IMP for other reasons than disease progression (e.g., adverse events), every effort should be made to continue on-trial radiological evaluation according to protocol until disease progression, start of a new anti-cancer treatment, withdrawal of consent or death (see [Table 11](#)).

Document Name: GCT1021-01 Protocol

Document Number: TMF-03326

Version: 11.0

---

If reduction of target lesions  $\geq 30\%$  in size is observed a repeat CT-scan will be performed after 4 (in particular for the 3Q4W-arm) to 6 weeks (in particular for the 1Q3W-arm) to confirm the response.

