For the dose-escalation part, all seven dose levels from the 1Q3W regimen together with a 'total' will be presented on one page. And similar for the 3Q4W regimen in the dose-escalation part, all four dose levels will be presented together on one page including a 'total'.

For the expansion part the following grouping should be done: Cohorts 1, 3, 4, 5, 6 and 7 on one page and cohort 2 with 2.2 mg/kg, cohort 2 with 1.8 mg/kg, cohort 2 total, cohort 8, total across 1Q3W and total across 3Q4W on one page.

All data will be listed by trial part, cohort for expansion part, dose schedule, dose level, subject number and visit (if applicable).

In general, in plots where subject data are grouped together (e.g. plots of means), the ticks on the time-axis will denote the nominal visit numbers (e.g. Scr, C1D1, C1D2, C1D4 etc.) separated with distances proportionate to the difference between the time-points of the corresponding visits in the relevant dose schedule (cf. the Visit Number and Day/Week rows of table of assessments in section 8 of the protocol final version 10.0, dd. 9 December 2019). Unscheduled visit data will not be included. In plots where individual subject data are plotted vs. time, the time on the horizontal axis will denote the actual time since C1D1. Unscheduled visit data will be included in these plots.

In tables and listings presenting data by visit, the visit names (Screening, Cycle 1 Day 1, Cycle 1 Day 2, ..., End of Treatment, Safety Follow-up, Subject Follow-up and End of Trial) will be used or their abbreviated term (Scr, C1D1, C1D2, ..., EOTrt, Saf FU, Pat FU, EOTrial).

In tables and listings presenting coded data (medical history, prior and concomitant medications, adverse events, prior and subsequent cancer therapies), the dictionary and the version used will be mentioned in the footnote.

When data until a certain date needs to be included in the analysis, the cut-off date will be defined as this date. If no cut-off needs to be applied, the cut-off date will be defined as the date of data extraction.

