4.5.2 Expansion Part

- Enapotamab vedotin: schedule and dose from the dose-escalation part recommended by the DMC and confirmed by the sponsor safety committee based on benefit-risk assessment.
 - Cohort 1: NSCLC subjects with classical sensitizing EGFR mutations and/or EGFR mutations targeted by third generation TKIs - 1Q3W schedule, 2.2 mg/kg
 - Cohort 2: NSCLC subjects without activating EGFR mutations or ALK rearrangements - 1Q3W schedule, 1.8 mg/kg or 2.2 mg/kg
 - Cohort 3: Melanoma subjects with BRAF V600 mutation 1Q3W schedule, 2.2 mg/kg
 - Cohort 4: Melanoma subjects with BRAF V600 wild-type 1Q3W schedule, 2.2 mg/kg
 - o Cohort 5: Sarcoma subjects 1Q3W schedule, 2.2 mg/kg
 - Cohort 6: Subjects with solid tumors, excluding NSCLC, melanoma, ovarian cancer and sarcoma subjects unless having a known AXL gene amplification (preferably no more than 8 subjects should be recruited for one tumor type) - 3Q4W schedule, 1.0 mg/kg
 - Cohort 7: Platinum-resistant ovarian cancer subjects 1Q3W schedule, 2.2 mg/kg
 - Cohort 8: NSCLC subjects without activating EGFR mutations or ALK rearrangements - 3Q4W schedule, 1.0 mg/kg

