15.1.4 Progression-Free Survival according to RECIST 1.1

PFS is defined as the number of days from the date of first IMP administration to first PD or death whichever occurs first.

PFS will be derived for all subjects and presented graphically as well as summarized using survival analysis methods:

- Kaplan-Meier curves
- Kaplan-Meier curves by subgroups defined for cohorts 2 and 8 and for cohort 6 as mentioned in section 4.4
- Kaplan-Meier estimates.
- Kaplan-Meier estimates by subgroups defined for cohorts 2 and 8 and for cohort 6 as mentioned in section 4.4.

PFS will be censored in accordance with Table A in Appendix 3 in the FDA Guidance for Industry "Clinical Trial Endpoints for the Approval of Cancer Drugs and Biologics (2007)".In summary, PFS will be censored if no event (progression or death) is observed before the first of (i) the analysis cut-off date, and (ii) the date when a new anti-cancer therapy is started. The censoring date will be the date of the last adequate tumor assessment prior to cut-off/start of new anti-cancer therapy. In case of an event after 2 or more missed scans, censoring will be done at last adequate tumor assessment date before the missed scans (Censoring rule based on FDA guideline). Two scans are considered missing if no evaluable response result (CR, PR, SD or PD) is available within a period of 98 days (6+1 weeks times 2) for 1Q3W dose schedule and a period of 126 days (8+1 weeks times 2) for 3Q4W dose schedule.

[figure not shown]

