15.1.6 Duration of Confirmed Response (RECIST 1.1) - Expansion Part

Duration of confirmed response (DoR) is defined as the number of weeks from the first documentation of confirmed objective tumor response (CR or PR) to the date of first PD or death. DoR will be analyzed using the same statistical methodology as PFS and the same censoring rules based on the FDA guideline, see section 15.1.4. DoR will be presented using confirmed responses only. Both the response assessments from the investigator will be presented.

15.1.7 Time to RECIST 1.1 and CA-125 combined response (Ovarian cancer only) – Expansion Part

Time to first RECIST 1.1 and CA-125 combined response (see Table 5 above) will be presented using the same statistical methodology as for ToR. CA-125 evaluation criteria (see section 15.1.2) should be fulfilled for CA-125 response evaluation, but not for RECIST 1.1 response evaluation (hence if they are NE based on CA-125, ovarian subjects are considered non-responder for CA-125 before defining the combined output). Both the response assessments from the investigator will be presented. The analysis will be performed for confirmed responses based on RECIST 1.1 only.

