2.1 Planned Analyses

Data collected up to and including the data cut-off date of 22 March 2021 has been reported in the CSR as per SAP version 4 dd. 30 June 2021. Data collected after the 22 March 2021 data cut-off date until the end of trial (last patient end of safety follow-up on 12 November 2021) will be reported in an addendum to the CSR based on the reporting described in this SAP addendum. This reporting in the addendum to the CSR includes data from the 3 subjects who remained on treatment after 22 March 2021 as well as data from the 47 subjects who remained in the (survival) follow-up period after 22 March 2021.

Populations will be defined as described in the SAP version 4 dd. 30 June 2021. Programs from the main analyses will be reused with the same definitions and decision rules except for the definition of what constitute an AESI in the CSR Addendum.

Following outputs will be repeated from the main analyses:

- Subject disposition
- Progression free survival
- Overall survival
- TEAE by PT
- Drug-induced liver injury
- All listings of all data after the cut-off date of 22 March 2021

The following output will be added

- Time to onset of first TEAE (AESI only),
- Time to resolution (AESI only); with percentage of events with outcome of resolution
- Time to improvement of TEAE (AESI only), percentage of events with improvement; with percentage of events with improvement
- AE summary table (same categories as in the main CSR but with the AESI categories as described below and AESI leading to permanent discontinuation of the trial treatment added)
- TEAE by PT and maximum grade
- TEAE of special interest by AESI type and PT

Page 3 of 8

TPL N°: eTPL SA-02-01 Of SOP SA-02.08 TPL Effective Date: 31 Mar 2016

- TEAE of special interest by AESI type, PT and highest NCI-CTCAE Grade
- Enapotamab Vedotin Related TEAEs of Special Interest by AESI Type and PT
- NCI-CTCAE grade >= 3 TEAEs of Special Interest by AESI Type and PT
- Serious TEAEs of Special Interest by AESI Type and PT
- TEAEs of Special Interest Leading to Permanent Discontinuation of Trial Treatment
 by AESI Type and PT

The definition of AESI in the CSR Addendum:

- PN: AEs with PTs within the peripheral neuropathy MedDRA SMQ: Peripheral neuropathy SMQ [20000034] (Broad)
- Constipation: PT
- Neutropenia: PTs neutropenia, neutrophil count decreased and febrile neutropenia.

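### The two-missed-scans censoring window follows dose schedule instead of scan interval, so Cohort 8 gets 126 days where the SAP's own formula gives 98

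*SAP*

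**What the plan says.** SAP 15.1.4 follows the FDA censoring table. An event after two or more missed scans is not counted, and PFS is censored at the last adequate assessment before the gap. Two scans count as missed when no evaluable response is available within 98 days (6+1 weeks, doubled) on 1Q3W, or within "a period of 126 days (8+1 weeks times 2) for 3Q4W dose schedule". No cohort is excepted, either there or in the SAP addendum.

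SAP 15.1.6 carries the rule into duration of response: "DoR will be analyzed using the same statistical methodology as PFS and the same censoring rules based on the FDA guideline".

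SAP 4.5.2 places Cohort 8 on the 3Q4W schedule: "Cohort 8: NSCLC subjects without activating EGFR mutations or ALK rearrangements - 3Q4W schedule, 1.0 mg/kg".

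Protocol Table 11, footnote 7, sets expansion imaging "every 6 (1Q3W and Cohort 8 3Q4W) or 8 (Cohort 6 3Q4W) weeks", and protocol 8.4.7 gives the same intervals, with a ±7-day window. For the 3Q4W dose escalation, protocol Table 10, footnote 8, says: "Radiological assessments are to be performed every 8 weeks from CID1".

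**The concern.** The 6 and the 8 in the SAP formula are scan intervals, and the added week is the scan window. Dose schedule is a sound proxy for scan interval everywhere except Cohort 8, which the protocol singles out as 3Q4W with 6-weekly scans. That cohort therefore gets a limit built for an interval it does not use.

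Cohort 8 studies the 3Q4W schedule in the Cohort 2 population, with the same scan interval as Cohort 2. SAP section 4 puts the two side by side in the outputs ("cohort 2 total, cohort 8, total across 1Q3W and total across 3Q4W on one page"), so readers will compare them. A patient who dies 110 days after the last adequate scan is censored in Cohort 2 and counted as an event in Cohort 8. Part of any PFS or DoR difference between the cohorts would then come from the endpoint definition. Response rate and overall survival do not use this rule.

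**Working it through.** **Inputs.** The window formula is from SAP 15.1.4, the schedule from SAP 4.5.2, and the scan intervals and ±7-day tolerance from protocol 8.4.7, Table 10 and Table 11.

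**Step 1: reproduce the SAP figures.** Window in days = (interval in weeks + 1) × 2 × 7.
- 6-week interval: (6+1) × 2 × 7 = 98. Matches.
- 8-week interval: (8+1) × 2 × 7 = 126. Matches.

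**Step 2: apply the formula to Cohort 8.** The interval is 6 weeks, so the window is 98 days. The SAP assigns 126, which is 126 − 98 = 28 days too long.

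**Step 3: see what each limit separates.** The gap between two obtained scans is interval × (missed + 1), with each scan up to 7 days early or late, so ±14 days in total.

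| Interval | Scans missed | Nominal gap (days) | Range (days) |
|---|---|---|---|
| 6 weeks | 1 | 84 | 70–98 |
| 6 weeks | 2 | 126 | 112–140 |
| 6 weeks | 3 | 168 | 154–182 |
| 8 weeks | 1 | 112 | 98–126 |
| 8 weeks | 2 | 168 | 154–182 |

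Censoring gaps above 98 days separates one from two missed scans exactly when scans are 6-weekly. Censoring gaps above 126 days does the same when they are 8-weekly. Applied to 6-weekly scans, 126 days falls on the nominal two-missed gap and splits those cases.

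**Step 4: size of the split.** Let each scan fall uniformly on any whole day from −7 to +7 (an assumption).
- Progression found after two missed 6-weekly scans: P(gap > 98) = 1 and P(gap > 126) = 0.467. The 126-day limit therefore keeps 53% as events, where the stated rule would keep none. If a gap of exactly 126 days is also censored, 47% are kept.
- Scans clustered nearer schedule (normal, SD 1 to 3.5 days): 54% to 64% are kept if only gaps above 126 are censored, and 36% to 46% if 126 itself is censored. With scans exactly on schedule the figure is 100% or 0%.
- Death, uniform between the second missed scan and the next scheduled one: 65–67% are censored at 98 days and 4–6% at 126.

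**Step 5: likely effect on the trial.** The documents give no missed-scan counts, so this rests on assumptions: 37 patients (the Cohort 8 maximum in protocol Table 1), exponential PFS with a 3-month median, 6-weekly scans and progression events only.

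| Scans missed or not evaluable | Mean progressions reclassified (censored if > 126 / if ≥ 126) |
|---|---|
| 5% | 0.10 / 0.08 |
| 10% | 0.35 / 0.33 |
| 20% | 1.20 / 1.03 |

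At 20% missed, the 5th to 95th percentile of the difference in 6-month PFS stays within about 2 points either way. Adding deaths leaves it there.

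**The case against.** The strongest reply is that this hardly matters. PFS and DoR are secondary endpoints with no planned test, no formal comparison of Cohorts 2 and 8 is specified, and protocol 10.2.3 has dosing regimens analysed separately. Under the Step 5 assumptions no progression is reclassified in about 90%, 67% and 32% of simulated trials at 5%, 10% and 20% missed. Thirty-seven is the maximum enrolment; at 22 patients the means fall to 0.06, 0.21 and 0.72. The shift can go in either direction. Development has stopped and the main data are already reported.

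All of that stands as a limit on the size, but none of it makes 126 days right for Cohort 8.

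Three smaller points also have force:
- The absence of this choice from SAP 4.9 proves little. That section lists departures from the protocol, and protocol 10.4.2 gives no day count to depart from.
- A result on day 126 is ordinarily within a 126-day period, so censoring only gaps above the limit is the natural reading. It is also the reading under which both limits separate one from two missed scans exactly.
- The gap calculation uses scheduled scans only, whereas protocol 8.4.7 calls for earlier imaging when progression is suspected. That would shorten some gaps.

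**Conclusion.** The concern holds. The Cohort 8 window is 28 days longer than the SAP's own formula gives, and under it the rule no longer does what SAP 15.1.4 says: about half of progressions after two missed scans stay as events. That conclusion follows from the two documents, although the exact share depends on how scans scatter around their due dates.

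The effect on results is probably small, about 0.1 to 1.2 reclassified progressions and no more than about 2 points on 6-month PFS. Those figures rest on assumed enrolment, median PFS and missed-scan rates. DoR has fewer subjects, so a single change could be more visible there. The 126-day limit is correct for Cohort 6 and the 3Q4W escalation. This should be corrected, but it does not threaten the trial's main conclusions.

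**What to change.** In SAP 15.1.4, define the window by scheduled scan interval: 98 days for all 6-weekly subjects, including Cohort 8, and 126 days for 8-weekly subjects (3Q4W escalation and Cohort 6). State that only gaps longer than the limit are censored.

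This takes one sentence and one parameter by cohort. The addendum records that data to the "data cut-off date of 22 March 2021 has been reported in the CSR as per SAP version 4", so the correction also needs a small rerun, labelled post hoc: PFS (with the Cohort 8 subgroup outputs) and DoR, for Cohort 8 and the 3Q4W total. Start by counting Cohort 8 subjects whose event came 99 to 126 days after the last adequate scan, and report that number. If it is zero, the estimates do not change and one line closes the matter. The cost is that any such events become censored.

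A minor point for the addendum, which reuses the same PFS method and concerns at most the 3 subjects still on treatment: Amendment 10 moves 1Q3W and Cohort 8 to 12-weekly scans, for which the formula gives (12+1) × 2 × 7 = 182 days. The window should use the interval in force, with a rule for gaps that span the change. The Cohort 6 interval must be reconciled first. The Amendment 10 summaries in protocol 8.4 and Appendix VI give 12 weeks without exception, while Table 31 footnote 7 and section 16.2.7 keep 8 weeks for that cohort.

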15.1.5 Time to Confirmed Response according to RECIST 1.1 - Expansion

Time to Confirmed Response (TOR) is defined as the number of weeks from date of first IMP administration to the date of first response (CR or PR) according to RECIST 1.1. Only responders will be included in the analyses (no censoring). TOR will be analyzed using the

Page 25 of 46 TPL N°: eTPL SA-02-01

TPL Effective Date: 31 Mar 2016 Approved in Vault: 6/30/2021

Of SOP SA-02.08

same statistical methodology as PFS. For these analyses, only confirmed responses will be used. Both the response assessments from the investigator will be presented.

Version: 4.0

The time to event graph of TOR will represent only confirmed responders and will start from the bottom-left corner (no responders) to the top-right corner.

